10.3 Statistical analysis plan

10.3.1 Summary of baseline data and flow of patients

This study uses a multiple single case series design, a form of Single Case Design (SCD). It will employ quantitative methods to track changes in personality functioning over time using the LPFS 2.0 scale and changes in loneliness using the Social Isolation Short Form 4a. Data from a participant will be compared within the participant between treatment phases (baseline, treatment and follow up), so participants serve as their own controls.

There is no comparison between groups possible nor necessary in this design.

10.3.2 Primary outcome analysis

Primary outcome measures are personality functioning, using the LPFS 2.0 scale, and changes in loneliness, using the Social Isolation Short Form 4a. These measures will be filled out on a weekly basis. The line graphs of the data will be inspected visually first, to see the pattern of observations. We will analyse for trend (progress over time), level of change and stability (variability) within the three phases using within-condition and between-condition visual inspection analyses. The median, median regression, stability envelope of the regression and TAU-U (Parker et al. 2011) will be calculated for each phase, with the median level of change chosen to mitigate the influence of outliers in the data. We will test the hypothesis that the median in the baseline phase exceeds the medians of the treatment and follow-up phase. In addition, non-parametric randomisation tests will be used to statistically evaluate the difference in mean and median scores of the phases statistically. The permutation distance test (Vroegindeweij et al. 2023) will be used since this randomisation test corrects for autocorrelation before the permutation test takes place. In this test a p-value is calculated

for every participant. Moreover, a p-value for the group will also be calculated using the property of p-values that they are uniformly distributed under the null-hypothesis. Using this property, the p-value of the group effect is the probability of a series of individual p-values given the null hypothesis (Onghena et all. 2005). In this test a range of baseline lengths, i.e. the number of baseline measurements, is determined and participants are randomly assigned to one of these baseline lengths. In this test a null distribution of 1000 mean differences is calculated and it is counted how many of the random mean differences is as extreme or more extreme than the observed mean difference (Bouwmeester, 2021).

Service use and self-harm data will be compared between the treatment phases with nonparametric test for repeated measures (Friedman Test), depending on the fulfilment of the requirements for parametric test.

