3.4 Primary endpoint/outcome

Reductions in the LPFS 2.0 and Social Isolation short form 4.0 constitute a potential benefit. We have chosen these outcome measurements as they are used internationally, recommended by ICHOM, and have been validated for use in older adults. We are measuring personality functioning and social isolation as our primary measures. We are making comparisons between baseline functioning, and across participants to power the study. Measurements are taken weekly from start of the waiting period, for the duration of the treatment phase, and at follow up.

The primary endpoint will be whether personality function (as measured by the LPFS 2.0) and social isolation (as measured by the social isolation short form 4.0) have changed during 24 months. Significant decreases in both measures will indicate that MBT is effective at improving personality functioning and decreasing social isolation.

Additionally, if participants had any incidents of suicidal behaviour or self-harm, then a reduction in frequency of these events will constitute a potential benefit. As older people may keep suicidal behaviour and self-harm hidden, there is an expectation that participants may not make disclosures around these issues at baseline.

Taking data pertaining to service use may provide a limited indication as to whether any potential cost savings are associated with the intervention. Due to the limited number of participants, there is a recognition that statistical test on these findings may not reach statistical significance.

Any reduction in self-harm, suicidality, or service use may also represent efficacy.

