4 TRIAL DESIGN

Design:

This study uses a multiple single case series design, a form of Single Case Design (SCD). It will employ quantitative methods to track changes in personality functioning over time using the LPFS 2.0 scale and changes in loneliness using the Social Isolation Short Form 4a. Data from a participant will be compared within the participant between treatment phases (baseline, treatment and follow up), so participants serve as their own controls. Initial data collection will take place at an outpatient clinic in Manchester, United Kingdom. Data will be gathered weekly away from the MBT clinic. The research team, primarily involved in clinical practice, will utilize an established older adult MBT service in Manchester for the sample. This approach mitigates some challenges of assessing multi-modal

psychological treatments, as there's no need for the research team to establish a new therapy program.

A multiple single case series design will enhance experimental control since participants serve as their own control. In order to get a stable and representative estimate of the baseline state all participants will have a waiting period of 8 weeks before starting treatment. Participants who drop out of the research completely during this phase won't have any further data collected We will ask anyone who drops out of the therapy to consent to providing data relating to their reason for drop out.

The strength of a SCD study is that it produces statistical power by taking a large number of data points with a small number of participants. Due to the high number of data points per participant, change to outcome measurements can accurately be described. Additionally, due to the low number of participants, there is a lower cost to the intervention, which means that it is more feasible to carry out long term studies of psychological treatments for personality disorder, which often span multiple years.

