10 STATISTICS AND DATA ANALYSIS

10.1 Sample size calculation

We used an app that was designed to calculate power in multiple single case series studies (Single Case Designs (architecta.shinyapps.io/SingleCaseDesigns v3/). A permutation distance test, which is useful in this design because it corrects for auto-correlation, showed that with sample size of 10 and Cohen's d of 1 the power is close to 1. We are expecting some participants may drop out of the study, and so aim to recruit 14 potential participants.

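### The primary test has no time term, so downward drift over the 80 weeks would be read under Section 3.4 as MBT being effective

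*Protocol*

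**What the plan says.** Section 10.3.2 states the hypothesis as a comparison of levels: "We will test the hypothesis that the median in the baseline phase exceeds the medians of the treatment and follow-up phase". Randomisation tests are added to "statistically evaluate the difference in mean and median scores of the phases". Their reference distribution is built from mean differences ("In this test a null distribution of 1000 mean differences is calculated"), and the p-value counts "how many of the random mean differences is as extreme or more extreme than the observed mean difference". The stated correction is for autocorrelation.

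Trend is not ignored. The same section describes it for each phase by visual inspection, median regression with a stability envelope, and Tau-U. None of these is tied to the test or to the conclusion.

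Section 4 relies on within-person comparison, "so participants serve as their own controls". Section 10.3.1 says that a comparison between groups is neither possible nor needed, and Section 10.5 marks adjusted analysis as not applicable. Section 3.4 sets the reading: "Significant decreases in both measures will indicate that MBT is effective at improving personality functioning and decreasing social isolation".

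One sentence of 10.3.2 has participants randomised to one of a range of baseline lengths. The trial flow chart, Section 4, the Section 7 table and Appendix 4 all give everyone 8 weeks or 8 measurements.

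**The concern.** The implied model is score = person level + phase effect + autocorrelated error. The null hypothesis being tested is therefore no change over the observation period, whereas the conclusion in 3.4 is about change caused by MBT. Correcting for autocorrelation does not remove a trend.

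The Protocol itself gives reasons to expect some drift. The baseline follows a 12-week MBT introductory group. Assessment work is under way during the baseline. Community team care continues, and other treatments are not restricted (Section 7.1). Because baseline weeks always come first, any steady or early fall makes the baseline higher than what follows. A trial with no effect of the treatment phase could then be reported as showing efficacy. An upward drift would do the opposite and hide a real benefit.

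**Working it through.** **Inputs from the Protocol.** 8 baseline, 72 treatment and 24 follow-up weekly measurements (Appendix 4); n = 10, with 14 recruited (10.1); phase difference and group p-value built from the individual p-values (10.3.2).

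**Assumed, because not stated.** Within-person SD 1; AR(1) 0.3; alpha 5%; one-sided, following the directional hypothesis; permutation of mean differences on every third week. The group p-value is taken from the sum S of the n individual p-values: P(S ≤ s) = (1/n!) Σ (−1)^k C(n,k)(s−k)^n over k ≤ s. Drift D is the total fall over the 80 weeks, either linear or early settling with a 12-week time constant. For the two-measure rule both scales drift and their errors correlate 0.5. Baseline is compared with treatment only.

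**1. The Protocol's own figure.** Section 10.1 states that "with sample size of 10 and Cohen's d of 1 the power is close to 1". Simulation with no drift and a 1 SD step gives group power 1.00 one-sided and 0.985 two-sided at AR(1) 0.3 (0.995 and 0.945 at AR(1) 0.5). The figure reproduces.

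**2. Phase gap produced by drift alone.** Number the weeks from 0.
- Linear: mean week is 3.5 in baseline, 43.5 in treatment and 91.5 in follow-up. Gap = D × (43.5 − 3.5)/80 = 0.5D for treatment and D × (91.5 − 3.5)/80 = 1.1D for follow-up if the drift continues.
- Early settling: the mean of exp(−t/12) is 0.761 in baseline and 0.089 in treatment, so the gap is about 0.67D.

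**3. Group test significant with no MBT effect, n = 10, one-sided 5%.**

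| Drift over 80 weeks | One measure, linear | One measure, early settling | Both measures, linear | Both measures, early settling |
|---|---|---|---|---|
| none | about 5% | – | 1-2% | – |
| 0.3 SD | 18% | 27% | 7% | 11% |
| 0.5 SD | 38% | 52% | 21% | 34% |
| 1 SD | 82% | 96% | 69% | 93% |

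Independent runs agree within simulation error and choice of thinning: for one measure with linear 0.5 SD drift they gave 33-39%.

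**4. Sidedness.** Two-sided rates per measure are about 10-15% at 0.5 SD and 30-58% at 1 SD. The two-sided rate for both measures cannot exceed these.

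**5. Upward drift.** A 1 SD rise adds 0.5 × 1 = 0.5 SD to the treatment mean, which cancels a true 0.5 SD benefit. Simulated group rejection (no autocorrelation) was 3.5%.

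**6. Tau-U corrected for baseline trend.** Within-baseline pairs: C(8,2) = 28. Between-phase pairs: 8 × 72 = 576. The correction can move the index by at most 28/576 = 0.049, so it would not cure the problem.

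**7. Segmented regression per participant** (intercept, time, level change, slope change), with a one-sided t test of the mean level change:
- about 4-6% false positives under linear drift;
- about 8-10% under early settling of 0.3-0.5 SD;
- about 90-93% power for a 1 SD step;
- about 6% power for a purely gradual 1 SD change over 80 weeks, against 81% for the permutation test.

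**8. Randomised start.** If baseline length were truly randomised (5-12 weeks assumed) and only that assignment re-randomised in the test, false positives under 1 SD linear drift were 4.5-6.8%. Power at d = 1 was about 0.78.

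**The case against.** The strongest objection concerns size. Section 3.4 requires decreases in both measures, so single-measure rates overstate the risk of the conclusion it draws. A reader might infer that a small drift of 0.1-0.2 SD already makes a false claim of efficacy common. The documents do not support that. Under the two-measure rule with n = 10, the rate passes 10% only at about 0.3 SD for early settling and between 0.3 and 0.5 SD for linear drift. With n = 14 and early settling it does so at about 0.2-0.3 SD. The count of results as extreme or more extreme also leaves sidedness open, and a two-sided test lowers the rates further.

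A reader might also infer that the plan disregards trend. It does not: a median regression per phase already describes level and slope. What is missing is any link from that description to the test or to 3.4.

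One sentence does describe random baseline lengths, which could protect the test. As scheduled, with 8 weeks for everyone, that protection is absent.

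Finally, this is a pilot that speaks elsewhere of potential benefit, has feasibility and acceptability among its primary outcomes, and is meant to inform the design of a later RCT. Nothing says that an RCT would be justified by this test alone. A trend-adjusted sensitivity analysis could also sit in a statistical analysis plan that is not shown. These points limit the consequence, but the efficacy reading in 3.4 stands in the Protocol as written.

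**Conclusion.** The point holds. The tests in 10.3.2 detect change over time, and 3.4 attributes that change to MBT without anything in the design or analysis that separates the two. Under the assumptions above (n = 10, one-sided), the chance that both measures are significant with no MBT effect rises from 1-2% without drift to about 7-11% at 0.3 SD, 21-34% at 0.5 SD and 69-93% at 1 SD.

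These figures rest on assumed drift, autocorrelation, alpha, sidedness and between-measure correlation, none of which the Protocol gives. A detrending option in the software cannot be excluded, but none is stated. The direction of the error does not depend on these values: a downward drift inflates the apparent effect and an upward one conceals benefit.

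**What to change.** 1. **Section 3.4.** Replace the efficacy sentence with one saying that significant decreases mean scores were lower during or after MBT than in the waiting period. Add that this is consistent with potential benefit but does not separate MBT from change over time.
2. **Section 10.3.2.** Beside the permutation result, prespecify a trend-adjusted estimate: time, level change and slope change fitted per participant, then averaged over participants with a confidence interval. Label it supporting, and do not make it a gate for claiming efficacy. State its limits: 8 baseline weeks make it imprecise, it is weak for gradual benefit, and early settling still inflates it somewhat. Align Section 10.5.
3. **Baseline length.** Reconcile the sentence on random assignment in 10.3.2 with the fixed 8 weeks in the flow chart, Section 4, the Section 7 table and Appendix 4. Only a genuinely randomised start, analysed by re-randomising that assignment, would itself protect the test against drift. If that is what is meant, the power statement in 10.1 needs to be redone for that test.

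Items 1 and 2 cost a few sentences and one regression on data already being collected. The cost of item 3 depends on which description is intended: a text correction if the baseline is fixed, a design change if it is randomised.

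### The primary analysis states a median hypothesis but describes a mean-difference test, and never says which statistic, phase contrast or p-value makes a scale's decrease significant

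*Protocol*

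**What the plan says.** Protocol 10.3.2 gives the primary hypothesis in medians: "We will test the hypothesis that the median in the baseline phase exceeds the medians of the treatment and follow-up phase". It prefers the median for level of change because of outliers ("with the median level of change chosen to mitigate the influence of outliers in the data"). It then plans tests on both statistics: "non-parametric randomisation tests will be used to statistically evaluate the difference in mean and median scores of the phases statistically". The only null distribution it describes is of means: "In this test a null distribution of 1000 mean differences is calculated".

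The same section yields p-values at two levels, one for each participant and one combined: "Moreover, a p-value for the group will also be calculated".

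Section 3.4 attaches a conclusion to the result: "Significant decreases in both measures will indicate that MBT is effective at improving personality functioning and decreasing social isolation". It defines the endpoint as change over 24 months. Section 3.3 says that period covers 18 months of treatment and 6 of follow-up, so the endpoint does not select a contrast.

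**The concern.** The two sections join only through the word significant, and that word is not tied to a result. On each scale there are two contrasts (baseline against treatment, baseline against follow-up) and two statistics (mean, median). That makes four tests, each available for every participant and for the group. The text also points both ways on the statistic: the hypothesis and the outlier argument favour the median, the description of the test favours the mean.

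The choice has consequences. The two contrasts answer different questions: gains made on treatment and lost afterwards would pass one and fail the other. Mean and median can disagree when a phase holds a few extreme weeks. If the analyst may take whichever version is significant, the error for that scale exceeds the nominal level. Individual p-values add a further route, because with ten or more participants some will be significant by chance.

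**Working it through.** **Inputs from the protocol.** 10 participants analysed, Cohen's d of 1 (10.1); 8 baseline, 72 treatment and 24 follow-up scores (Appendix 4); directional hypothesis (10.3.2); both scales required (3.4).

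**Assumptions.** One-sided alpha 0.05, since none is stated (0.025 also shown). Group p-value from the sum of the individual p-values. Correlation between scales 0, 0.5 or 0.8. The step that removes autocorrelation is approximated by fixed thinning. Simulation error on single rates is about 0.5 to 1 point.

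**Method.** Each participant's p-value is the share of 199 random relabellings whose baseline-minus-later difference is at least the observed one, with the observed value counted in numerator and denominator. The group p-value for n = 10 with sum s of individual p-values is

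P(S ≤ s) = (1/n!) Σ_k (−1)^k C(n,k) (s − k)^n, over k ≤ s.

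**Step 1: the protocol's own figure.** At d = 1 and n = 10, simulated group power is 0.98 to 1.00 at alpha 0.05, for weekly autocorrelation 0 to 0.7 and thinning to every 1 to 4 weeks. The stated power of nearly 1 reproduces. Power for one participant is only 0.34 to 0.84.

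**Step 2: error when nothing changes, group level, alpha 0.05.** The first four result columns are per scale. The last applies the 3.4 rule with any of four allowed on each scale.

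| Scores per phase | Single test | Any of four | Both contrasts, mean | Both contrasts, median | Both scales |
|---|---|---|---|---|---|
| 8/72/24, near-continuous, scale correlation 0.5 | 4.3–4.9% | 9.9% | 2.2% | 2.0% | 2.7% |
| 4/36/12 (thinned), correlation 0.5 | 4.3–5.1% | 9.7% | 2.4% | 2.2% | 3.1% |
| 8/72/24, near-continuous, correlation 0 | 4.5–5.4% | 10.6% | 2.3% | 2.4% | 1.0% |
| 8/72/24, whole points (SD 3), correlation 0.8 | 1.3–3.7% | 6.1% | 1.7% | 0.5% | 2.9% |

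Whole-point scores give lower rates because ties make the permutation p-values conservative, most of all for the median. Four independent tests would give 1 − 0.95^4 = 18.5%; the four here overlap heavily. At alpha 0.025, any of four gives 5.1 to 5.7% (3.0% with whole points).

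**Step 3: the effectiveness claim.** If neither scale changes, the both-scales rule holds the error at 1.0 to 3.1% even with free choice within each scale. If one scale truly improves at d = 1, its half of the rule is met with probability 0.98 to 1.00. The error of the joint claim is then close to the other scale's own error, about 6 to 10%.

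**Step 4: participant level.** The chance that one given participant is significant on any of the four tests of a scale is 8.1% (whole points) to 11.7%. For at least one of ten:

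- 1 − (1 − 0.081)^10 ≈ 57%
- 1 − (1 − 0.117)^10 ≈ 71%
- one fixed test at exactly 5%: 1 − 0.95^10 = 40%

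**The case against.** The strongest reply is that the protocol already contains the safeguards. Section 3.4 requires both scales, and the hypothesis in 10.3.2 joins treatment and follow-up with *and*, which can be read as requiring both contrasts. On that reading the error per scale is about 2%, below nominal. Alpha, test hierarchy and descriptive labels are also often left to a separate SAP, which may exist. Much of this stands. The both-scales rule does protect the claim when neither scale changes, and the absence of an alpha would not be a finding alone. But nothing in 3.4 or the rest of 10.3.2 confirms the joint reading of the contrasts. A median hypothesis beside a mean-difference null is a conflict in the stated text, not a detail deferred.

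A reader might also infer stronger points that the documents do not support:

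- **That participant-level error is about 65%.** A figure of that size is the chance that at least one of ten participants is significant on some test. One participant's error is about 8 to 12%, and ten looks at a single test already give 40%. Nothing in the protocol lets one significant participant establish a significant decrease.
- **That Tau-U is another route to significance.** It is listed with the median, median regression and stability envelope as a per-phase summary, before the randomisation tests are introduced separately. It reads as descriptive.
- **That the power statement in 10.1 is wrong.** It refers to a sample of 10, which points to the group test, and it reproduces.

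**Conclusion.** The point holds as an inconsistency and an unfixed decision rule, with a conditional effect on error. Hypothesis and described test use different statistics, and no result is named as deciding for a scale. At an assumed one-sided alpha of 0.05, if any of the four group tests counts, the error per scale is about 6% (whole-point scores) to 10% (near-continuous scores).

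It would go too far to say that the false-positive rate of the effectiveness conclusion is doubled outright. That rate reaches about 6 to 10% only when the other scale truly improves, which is plausible for two different constructs; when neither changes it is about 1 to 3%. With at least one of ten participants significant by chance in 57 to 71% of trials, individual p-values should not support the claim. These sizes rest on the assumed alpha, the sum-of-p combination and the thinning approximation.

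**What to change.** Amend 3.4 and 10.3.2 together:

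- Use one statistic, mean or median, for both the hypothesis and the permutation test, and report the other as description.
- State alpha, make the group p-value the deciding result on each scale, and label individual p-values descriptive.
- Say that a scale's decrease is significant only if baseline against treatment and baseline against follow-up are both significant, as the hypothesis wording suggests (about 2% error per scale). Alternatively, name one deciding contrast in advance; a single fixed group test gave 4.3 to 5.4% with near-continuous scores.
- Keep the both-scales rule of 3.4.

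Which contrast should lead, if only one is chosen, is for the investigators: the 24-month endpoint spans both phases. Section 10.1 needs no change.

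The cost is protocol wording only. A result seen in only one participant or one contrast could no longer be called proof of effectiveness, but could still be reported as a potential benefit, which suits a pilot.

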7 TRIAL PROCEDURES

Process	Time
Community Mental Health Teams, and Therapy Hub Teams are notified of recruitment by poster, visits to team meetings, and email.	Prior to commencement of study
CMHT or Therapy Hub staff to discuss the trial with existing patients of the CMHT service. CMHT staff will gain consent for the trial team to contact the participant.	Prior to the commencement of study
Participant contacted by trial team. Brief information about trial provided. If participant is provisionally interested in joining the study, then they will be offered an initial appointment to be given the full participation information leaflet.	Prior to the commencement of study
Following the initial meeting, the participant will be given 7 days to decide if they want to be part of the trial.	0 days

After 7 days, the participant will be invited back to sign informed consent forms or withdraw from the study.	At 7 days
Participant contacted to advise them of the date of the introductory group.	At 1 months
Participants that complete the introductory group will become part of the baseline phase of the study.	At 4 months
Participants will have a baseline waiting period of 8 weeks. Outcome data will be collected during this phase. The participant will also start producing their MBT passport, and assessment collaboratively with a member of the treatment team.	At 8 months
Participants will begin MBT treatment for a period of 18 months. Outcome data taken weekly. Secondary outcomes and review of service use/self-harm taken every 6 months.	At 24-26 months
Follow up period will begin. Primary outcome data taken weekly.	Between 24-26 and 30-32 months
Qualitative interviews take place.	Between 30-34 months
Study end point. Data analysis and publication phase begins.	30-36 months
Dissemination of findings, publication.	Within 12 months following the last follow up data point of the final participant.

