16.4 Appendix 4 – Schedule of Procedures

Procedures	Visits (insert visit numbers as appropriate)				
	Screening	Baseline	Treatment Pha	se	Follow Up
Informed consent	2				
Demographics	1				
Medical history		1			
Assessment 1 (SCID-PD screen)	1				1
Assessment 2 (SCID PD full interview)	1				
Assessment 3 (Primary outcomes)		8	72		24
Assessment 4 (Secondary outcomes)		1	4		1
Assessment 5 (Qualitative interview)					1
Adverse event assessments		1			1

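### The combined group p-value tests whether anyone changed, not whether the average participant improved, yet section 3.4 reads significance as showing that MBT is effective

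*Protocol*

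**What the plan says.** Section 10.3.2 of the protocol calculates a permutation p-value for each participant after a correction for autocorrelation. It then forms a group p-value from the fact that p-values are uniform under the null: "Using this property, the p-value of the group effect is the probability of a series of individual p-values given the null hypothesis". The rule for combining them is not named. The hypothesis is directional, with baseline higher than treatment and follow-up.

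Section 3.4 gives the reading: "Significant decreases in both measures will indicate that MBT is effective at improving personality functioning and decreasing social isolation". Section 4 explains where the power comes from, saying of the design that "it produces statistical power by taking a large number of data points with a small number of participants". Section 10.1 reports that the permutation distance test "showed that with sample size of 10 and Cohen's d of 1 the power is close to 1".

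**The concern.** A group p-value built this way has a joint null: every participant has a true phase difference of zero. Rejecting it establishes that at least one person changed. It does not establish that the mean, or the typical participant, improved.

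The reason lies in the error term. Weeks are the replicates, so only within-person fluctuation is counted. Over 18 months of treatment and 6 months of follow-up, people may drift up or down for reasons unrelated to MBT. That variation between people in the amount of change is not in the calculation. A few large improvers could produce a significant group effect while the average change is nil. Section 2 says the study will inform a future RCT and help shape guidance, so a result of that kind reported as a group benefit would matter.

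**Working it through.** **Inputs from the protocol.** N = 10 analysed, d = 1 and power close to 1 (10.1). Baseline of 8 weeks (section 7: "Participants will have a baseline waiting period of 8 weeks"). Primary outcome measurements of 8 at baseline, 72 in treatment and 24 in follow-up (Appendix 4). Directional hypothesis (10.3.2), taken as one-sided.

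**Assumed, because the protocol does not state them.** Alpha 0.05; combining rule (sum or product); week-to-week autocorrelation 0–0.5; between-person SD of true change, tau, of 0.25–1.0 in units of the within-person SD.

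**Step 1: one person.** D = baseline mean − treatment mean. With independent weeks, SE = √(1/8 + 1/72) = √0.1389 = 0.373 within-person SD. With first-order autocorrelation 0.5, SE = 0.589. The one-sided p is 1 − Φ(D/SE).

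**Step 2: the group.** Sum rule: reject if the ten p-values sum to 3.496 or less (exact 5% point of a sum of ten uniforms). Product rule: reject if −2Σln p ≥ 31.41 (chi-square, 20 df).

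**Step 3: the plan's own figure.** With a common shift of d = 1 (tau = 0), power under the sum rule is 1.00 at autocorrelation 0 to 0.5 and 0.99 at 0.7. Close to 1 is reproduced.

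**Step 4: average change zero, people differ.** True changes are drawn from N(0, tau²), so D/SE has SD √(1 + tau²/SE²). At tau = 0.5 with independent weeks this is √(1 + 0.25/0.1389) = 1.67 instead of 1. Simulated rejection rates per scale (100,000 trials per cell):

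| tau | Sum, autocorr. 0 | Sum, autocorr. 0.5 | Product, autocorr. 0 | Product, autocorr. 0.5 | Person-level t |
|---|---|---|---|---|---|
| 0 | 5% | 5% | 5% | 5% | 5% |
| 0.25 | 7% | 6% | 14% | 8% | 5% |
| 0.5 | 10% | 8% | 41% | 20% | 5% |
| 1.0 | 13% | 11% | 80% | 56% | 5% |

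An actual permutation test on independent data with the sum rule gave 4.0%, 7.8%, 8.9% and 12.9% at tau 0, 0.3, 0.5 and 1.0. Comparing 8 baseline with 24 follow-up weeks gives 7.1%, 9.1% and 12.6% at tau 0.3, 0.5 and 1.0. N = 14 changes the sum-rule rates little. As tau grows, each p-value tends to 0 or 1, and the sum rule rejects when at most three are 1: (1 + 10 + 45 + 120)/1024 = 17.2%.

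**Step 5: both scales, as 3.4 requires.** Sum rule, independent weeks, the same assumed correlation between scales for true change and for noise:

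| Correlation | tau 0.5 | tau 1.0 |
|---|---|---|
| 0 | 0.9% | 1.8% |
| 0.5 | 2.8% | 4.2% |
| 0.7 | 4.1% | 5.8% |
| 0.9 | 6.3% | 8.4% |

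Under the product rule with independent weeks, the joint rate runs from about 17% to 34% at tau 0.5 and from about 64% to 74% at tau 1.0 over the same correlations.

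**Step 6: power at mean change 1, autocorrelation 0–0.5.** The planned sum-rule test has 0.99–1.00 at tau 0.5 and about 0.90–0.93 at tau 1.0. A one-sided person-level t test on the ten differences has 0.98–1.00 and 0.81–0.86.

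**The case against.** The best defence is that nothing is invalid. The group p-value is defined under a null in which individual p-values are uniform, and under that null it rejects 5% of the time. Wherever the table shows more than 5%, some participants really have changed, so rejection is correct for the hypothesis tested. This stands. The fault is the mismatch between that hypothesis and the conclusion in 3.4.

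The two-scale requirement also stands as a counterweight. A reader might infer that the trial's effectiveness conclusion carries an inflated error rate. For the sum rule the documents do not support that, since the joint rate exceeds 5% only when the scales are highly correlated. Nor do they support quoting one inflation figure as a property of the plan: tau, alpha, autocorrelation and the combining rule are all assumptions here.

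A reader might also infer that the stated power collapses once responses differ. It does not: at tau 0.5 it is still close to 1, and the loss becomes material only near tau 1. Section 10.1 reports the output of an app whose inputs are not shown, so one cannot say what it assumed about variation between people.

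Finally, the study is a pilot, feasibility and acceptability are also primary, and individual p-values, medians, Tau-U and graphs will show who changed. That softens the consequence. It still leaves no planned group test in which participants are the replicates.

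**Conclusion.** The concern holds as a mismatch between test and conclusion. The group p-value supports the statement that at least one participant changed; section 3.4 uses it to say that MBT is effective. Read as a test of average change, the one-sided rate per scale is about 6–13% with the sum rule and about 8–80% with the product rule, for alpha 0.05, 8 v 72 weeks, autocorrelation 0–0.5 and tau 0.25–1.0. With both scales required, the sum-rule rate lies between below 1% and about 8% and may be under 5%; with the product rule it can be far higher. This should be fixed, but it does not invalidate the design or the individual analyses.

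**What to change.** For each scale, compute one phase difference per participant. Report the mean difference with a 95% CI and a person-level sign-flip, signed-rank or t test, and make these the basis for any statement about average benefit. Add counts of participants improved, unchanged and worsened. Keep the combined p-value in 10.3.2, worded as evidence that at least one participant changed, and reword 3.4 to match.

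In 10.1, say that power close to 1 applies to a common shift of d = 1, and give the power of the person-level test over a range of assumed between-person SDs: about 0.98–1.00 at 0.5 and 0.81–0.86 at 1.0.

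No new data are needed. The cost is a less favourable power statement if responses vary widely. With about 10 participants from one service, a person-level test also does not by itself secure generalisation to other older adults, and the report should say so.
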